#### **12.3.2 Adverse Event Reporting**

During the course of an adverse event, severity and/or causality and/or seriousness may change. For CRF documentation this adverse event represents one entity from onset to resolution and the worst of the observed categories shall be attributed. When event reoccurs after it disappeared, it should be handled as a new AE. However, AEs that occur intermittently can be recorded as one AE. Adverse

events will no longer be reported if the subject has another liver - directed therapy or starts chemotherapy.

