If there is a radiological discrepancy regarding findings of residual, recurrent or progressive disease, the site must submit the subject's de-identified images to the centralized radiology panel overseen at LHMC. The panel will make the final determination and notify the site investigator. Any additional ablative treatment, be it to repeat TACE or SBRT or other therapy will be determined at that time. All treatment will be individualized by subject at the discretion of the transplant team.

5.6 Additional local treatment to the target lesion(s) in the assigned treatment arm:

Group 1: SBRT (Arm A), subjects with residual disease or local recurrence ***in the previously treated lesion(s)*** on radiologic imaging at any point in follow up will be considered as having met the primary endpoint of the trial and they are off the study. Patients may be considered candidates for additional local regional therapy to the treated lesion of any kind per the discretion of the treating.

Group 2: TACE (Arm B), subjects with residual disease or local recurrence ***in the previously treated lesion(s)*** on radiologic imaging at any point in follow up will be considered as having met the primary endpoint of the trial and they are off the study. Patients may be considered candidates for additional local regional therapy to the treated lesion(s) of any kind per the discretion of the treating providers.

5.7 Patients in either group who develop new ***intrahepatic lesion(s)*** at any point in follow up will ***not have met the primary endpoint as they have not progressed at the site of previous treatment.*** They may be considered candidates for additional local regional therapy to the new site of disease ***of any kind*** per the discretion of the treating providers and will be followed per Table 4 thereafter.

5.8 If patients have no evidence of progression or residual disease in the treated lesion(s) ***but develop new tumors outside the previously treated field*** and, per the discretion of the treating providers, require treatment with systemic therapy, the patient will be censored from the data analysis for the primary endpoint and will be discontinued from the study.

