### **12.3 Adverse Event Guidelines**

#### **12.3.1 Adverse Event definitions**

- An Adverse Event is any untoward medical event that occurs in a subject who has received an investigational treatment, and does not necessarily have a causal relationship with the investigational treatment. An AE can therefore be any unfavorable and unintended sign (including abnormal laboratory finding), symptom, or disease temporally associated with the use of an investigational treatment, whether or not related to the treatment.
- Pre-existing diseases or symptoms or abnormal laboratory values present upon recruitment are not considered an AE even when observed during the further course of the study. However, every worsening of a pre-existing condition is considered an adverse event.
- All AEs  $\geq$  grade 3 will be collected and attributed either as possibly, probably or definitely related to protocol treatment or not related to protocol treatment. Additional AE's collected are, any grade  $\geq 2$  abdominal pain, nausea, vomiting, and fatigue. The NCI Common Terminology Criteria for Adverse Events Version 5.0 (CTCAE) will be utilized to grade AE's for AE reporting.

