## 14.0 Safety Variables

Adverse events will be captured throughout the study along with, physical exams and standard laboratory tests.

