#### 17.2.3 Other Secondary Endpoints

Quantitative outcomes like number of retreatments and number of toxicities will be described by mean, standard deviations, median, minimum and maximum by treatment group and treatment group will be compared using a t-test. Categorical outcomes like any retreatment, any toxicity, radiologic response, pathologic response will be described by counts, percent and groups compared using the chi-square test. Overall survival, and 60 day post-transplant morbidity and mortality will be described by Kaplan-Meier estimates, and groups compared using the log-rank test and Cox model as for the primary outcome. Note, with 98 patients per arm, each arm will have 99% and 95% probabilities of observing at least one event of toxicity when the true probabilities per patient are 0.05 and 0.03. Further, when estimating proportion of patients to have a particular toxicity, the 95% confidence intervals will have precision of 10% or tighter, for each treatment group.

We will analyze secondary endpoints relating to time to event analogously to time to recurrence, and quantitative outcomes analogously to the analysis the HRQL endpoints.

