### **Adverse events**

Adverse events will be described by body system and severity, on a per patient basis as well as a number per patient basis, and groups compared using chi-square and t-tests as appropriate.

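### Adverse-event observation ends with local failure or the next therapy, yet event totals are compared without allowing for time, which biases the toxicity comparison against the arm with longer control

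*Combined protocol and SAP*

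**What the plan says.** **When AE observation ends.** Section 12.3.2 stops it at further treatment: adverse "events will no longer be reported if the subject has another liver - directed therapy or starts chemotherapy". Section 5.6 says, for both arms, that a patient with residual disease or local recurrence in a treated lesion "will be considered as having met the primary endpoint of the trial and they are off the study". Section 12.2 also ends follow-up at transplant, apart from 60-day post-transplant status.

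**What is counted.** Section 12.3.1 defines an AE as an event that "does not necessarily have a causal relationship with the investigational treatment". It collects all grade 3 or higher events, plus four symptoms from grade 2. Neither analysis section limits the counts to events attributed to treatment.

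**How the arms are compared.** Section 17.2.3: "Quantitative outcomes like number of retreatments and number of toxicities will be described by mean" and other summary statistics, and "treatment group will be compared using a t-test". Any toxicity is compared by chi-square. The Adverse events paragraph describes events "on a per patient basis as well as a number per patient basis, and groups compared using chi-square and t-tests as appropriate".

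**What is absent.** No section gives an AE rate, person-time, a common window, or a time-to-first-AE analysis. The closing line of 17.2.3, which sends quantitative outcomes to the HRQL approach, adds no exposure adjustment.

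**A statement that does not fit.** Section 14.0: "Adverse events will be captured throughout the study along with, physical exams and standard laboratory tests". This is not reconciled with the stop rule in 12.3.2.

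**The concern.** The AE clock stops at the outcome that SBRT is meant to postpone. Any event that accrues over time, whether background illness in cirrhosis or late treatment effect, has more opportunity to be recorded in the arm with better control. A raw total or an any-event percentage then mixes toxicity with length of observation.

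Toxicity is a named secondary endpoint, and Section C gives possibly lower SBRT toxicity as part of the rationale. Under the plan as written, success on the primary endpoint would itself push the toxicity comparison against SBRT. Late events are expected: Section 10.3 lists possible long-term SBRT toxicities, and Table 4 schedules toxicity notation to 24 months.

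**Working it through.** **1. The plan's own figures.** The plan gives no figure for the AE comparison, so the related ones were checked first.
- Events at HR 0.6, two-sided 5%: 4(1.960 + 0.842)²/(ln 0.6)² = 120.3 for 80% power, and 161.1 with 1.282 in place of 0.842 for 90%. The plan states 120 and 161.
- SBRT median: 134/0.6 = 223 days, as in Table 7.
- Toxicity precision in 17.2.3: 1 − 0.95^98 = 99.3%; 1 − 0.97^98 = 94.9%; largest 95% half-width 1.96√(0.25/98) = 9.9 points. These agree with the plan, but treat every patient as equally observed.

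**2. Mean AE-reporting time.** Inputs: medians 134 and 223 days (Section 16.0, Table 7); 15% yearly dropout (Table 7); two-year cap (17.1); transplant taken as exactly 50% by two years (Section 16.0 says more than 50%). Hazards per day:
- Failure: λ = ln 2/134 = 0.00517 (TACE); ln 2/223 = 0.00311 (SBRT)
- Dropout: −ln(0.85)/365 = 0.00045
- Transplant: ln 2/730 = 0.00095

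With ω the sum of the other exit hazards, mean time = (1 − exp(−(λ + ω)·730))/(λ + ω).

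| Exits besides failure | TACE (days) | SBRT (days) | Ratio |
|---|---|---|---|
| Dropout, 2-year cap | 175 | 260 | 1.49 |
| Plus transplant | 151 | 214 | 1.42 |
| Plus failure dated at 91-day scans (simulated) | 188 | 245 | 1.30 |

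**3. Effect on counts.** Assume one treatment-period AE per patient and the same later rate r per patient-year in both arms. With 91-day scans the expected counts are 1 + r·188/365 and 1 + r·245/365. At r = 1 that is 1.52 against 1.67 (ratio 1.10); at r = 2, 2.03 against 2.34 (1.15); at r = 4, 3.06 against 3.68 (1.20).

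**4. Effect on the planned t-test.** Simulation with 98 per arm, Poisson counts, equal true rates, dropout, transplant and 91-day scans:

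| Later AEs per patient-year | False rejection (nominal 5%) |
|---|---|
| 0 | about 5% |
| 0.5 | about 7% |
| 1 | about 12% |
| 2 | about 24% |
| 4 | about 38% |

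When later AEs occur, the excess rejections are almost all against SBRT. If there are no treatment-period AEs at all, the t-test falsely finds more AEs on SBRT in 14%, 22% and 32% of trials at 0.5, 1 and 2 per year, and the chi-square on any AE does so in 13–15%. Overdispersion weakens the effect but does not remove it: under strong overdispersion, with background events only and failure dated continuously, the t-test still gives 19–24% at 1–2 per year.

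**5. Candidate remedies.**
- *Person-time offset alone.* With one treatment-period AE plus 1, 2 or 4 later AEs per year and failure dated continuously, it falsely favours SBRT in 35%, 31% and 24% of trials (rate ratio 0.80–0.89). Early events are divided by a longer denominator in the SBRT arm.
- *Six-month count whatever therapy follows.* By day 183, 1 − 2^(−183/134) = 61% of TACE and 1 − 2^(−183/223) = 43% of SBRT patients have failed locally, so toxicity of later therapy enters unequally.
- *Mean cumulative counts censored at the end of reporting.* False rejection stays at about 4–6.5%, using data already collected.

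**6. Patients left at six months.** Still under AE reporting at day 183: exp(−0.00657·183) = 30% of TACE (about 29 of 98) and exp(−0.00450·183) = 44% of SBRT (about 43 of 98). Comparisons at 3 and 6 months are feasible; much later ones would be thin.

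**The case against.** The strongest reply is that the size is assumed. The documents give no AE rate, and collection is limited to grade 3 or higher plus four grade 2 symptoms. The toxicities expected after TACE (10.1) and acutely after SBRT (10.2) are mainly treatment-period events. If all AEs were acute and equal between arms, the t-test would keep its 5%. Exits left out of the model (therapy for new lesions, extrahepatic disease, delisting, death) would tend to narrow the gap in observation time. This stands: it limits the size, but does not remove the dependence of AE observation on the primary outcome.

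A reader might infer that SBRT will show more AEs than TACE. The documents do not support that. Up to three TACE sessions can raise TACE counts and mask the bias, so the direction of the bias is known but the net difference is not.

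A reader might also infer from 12.3.2 that a second or third initial TACE ends AE reporting, leaving planned sessions unreported. Section 5.4 makes up to three sessions part of initial therapy, and Table 3 schedules toxicity notation at the later sessions and two weeks after them. Read together, these largely answer the point; what remains is an undefined term in 12.3.2.

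**Conclusion.** The concern holds as a bias in a stated direction. Followed exactly, the plan observes the arm with longer control for longer and then compares totals and any-event percentages as if observation were equal. The gap in mean AE-reporting time is about 1.3- to 1.5-fold on the planning values. Its effect on the t-test runs from none, if there are no later AEs, to about 38% false rejection at four later AEs per patient-year. The assumptions are exponential failure at the planning medians, constant dropout and transplant hazards, Poisson counts, one treatment-period AE per patient, and a later rate that the documents do not supply.

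**What to change.** In Sections 17.2.3 and Adverse events:
- Record each patient's AE-reporting end date and the reason for it.
- Replace the t-test and chi-square on raw totals with mean cumulative AE counts per patient by arm at fixed times (for example 3 and 6 months from randomization), with robust variance, censoring at the end of AE reporting.
- Add time to first AE of the analysed grade by cumulative incidence, with death and transplant as competing events.
- If rates per person-time are shown, treat them as supplementary and do not rely on them alone.

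In Section 12.3.2, define the therapy that ends AE reporting so that it agrees with Section 5.4 and Table 3, and reconcile the stop rule with Section 14.0.

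**Cost.** Slightly more analysis work, and one end date with a reason per patient; no extra visits. The method assumes that censoring at failure or next therapy is unrelated to later AE risk. That cannot be verified from these data and should be stated in the plan.

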#### 12.4 SAE Guidelines

12.4.1 A serious adverse event (SAE) shall be defined as an adverse event which fulfills one or more of the following criteria:

- Results in death
- Is immediately life-threatening
- Requires in-subject hospitalization or prolongation of existing hospitalization
- Results in persistent or significant disability or incapacity
- Is an important medical event that may jeopardize the subject or may require medical intervention to prevent one of the outcomes listed above
- **Any events or hospitalizations that are unequivocally due to progression of disease should not be reported as an SAE.**
- The causality of SAEs (i.e., their relationship to study treatment) will be assessed by the site investigators and will be labeled as either related to treatment, or not related to treatment.

12.4.2 Only adverse events deemed serious AND related will be reported to the IRB within 10 days of awareness of the event, or per institutional Policy. All other events will be noted in the subjects' medical record.

12.4.3 The following types of hospitalizations do not constitute SAEs:

- Hospitalization or Emergency room visits secondary to expected cancer morbidity.
- Admission for palliative care or pain management.
- Planned hospitalizations for surgical procedures either related or unrelated to the subject's cancer.

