Malagari et al conducted an open-label, single-center, single-arm study of DEB-TACE in 62 cirrhotic subjects with documented solitary unresectable HCCs. Mean tumor diameter was 5.6 cm (range, 3-9 cm) classified as Okuda stages 1 (n=53) and 2 (n=9). Subjects received repeat embolizations with doxorubicin-loaded beads every 3 months (maximum of three treatments). The maximum doxorubicin dose was 150 mg per embolization, loaded in DC Beads® of 100-300 or 300-500  $\mu$ m. Post-treatment, an objective response according to the European Association for the Study of the Liver (EASL) criteria was observed in 59.6%, 81.8%, and 70.8% across three treatments. At 9 months a complete response was seen in 12.2% of subjects. Severe procedure-related complications were seen in 3.2% (cholecystitis, n=1; liver abscess, n=1). Post-embolization syndrome was observed in all subjects (16). Several studies have since shown that DEB-TACE not only is favorable compared to conventional TACE regarding side effects but may elicit a better overall outcome. Song demonstrated in the Asian population a better treatment response and delayed tumor progression with DEB-TACE (17).

In a multicenter study including 201 European subjects (PRECISION V), use of DC Beads® resulted in a clinically and statistically significant reduction in liver toxicity and drug-related adverse events compared with conventional TACE with lipiodol and doxorubicin (18, 19). Two other trials reported higher rates of tumor response and longer time to progression for the loaded DC Bead as compared to a bland embolic microsphere with similar characteristics (20, 21). As a result of these investigations, DEB-TACE has been increasingly used as therapy for bridging treatment in subjects awaiting transplantation with HCC, although embolic beads without chemotherapy are also widely used (22).

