### **10.1 Expected Toxicities after TACE:**

- Abdominal pain
- Nausea
- Vomiting
- Fatigue

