### **10.3 Possible long term toxicities after SBRT:**

- Gastric or Bowel injury (ulceration, bleeding, perforation, fistula formation, or obstruction)
- Biliary obstruction due to inflammation or sclerosis
- Liver abscess
- Hepatic subcapsular injury
- Decreased renal function.
- Rib fracture
- Myositis
- Radiation-induced liver disease (RILD) including potentially fatal liver injury.
- In subjects who have Grade 4 elevation of liver enzymes levels and/or in subjects with early nonspecific signs or symptoms of liver injury, close follow-up is recommended with repeat blood work. If no tumor progression is documented in these subjects, liver injury will be presumed to be treatment related.

Only grade  $\geq 2$  toxicities will be considered in the statistical analysis. The following toxicities will require subjects to be removed from protocol treatment if the protocol treatment has not yet been completed. Patients will be followed per physician standard of care.

- Grade  $\geq 4$  hepatic toxicity for changes in AST, ALT, alkaline phosphatase, or platelet counts attributed to treatment and not attributable to disease progression. Transient grade 4 (less than 10 days) hepatic toxicities are acceptable.
- Grade  $\geq 4$  Upper GI bleeding (**attributed to treatment**, and not attributable to disease progression).
- Death due to any cause.

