#### 18.2 Role of Data Management

Lahey Hospital & Medical Center in conjunction with Quartesian will design and distribute source worksheets and the electronic data capturing system that will maintain all data collected as part of the protocol.

Data collection is the responsibility of the clinical trial staff at the site under the supervision of the site Principal Investigator. Collected study data must be promptly entered into the EDC system used by the Sponsor. Source worksheets should be used as the primary data collection instrument for the study, when possible. The investigator should ensure the accuracy, completeness, and timeliness of the data reported in the EDC and all other required reports. Data reported in the EDC, that are derived from source documents, should be consistent with the source documents and any discrepancies should be explained. Any missing data must also be explained. An audit trail will be maintained by the EDC system.

Sites are required to provide the Sponsor with de-identified source documents supporting the data entered into the EDC system within 1 week of each completed visit. Data must be shared via a Dropbox account approved by Lahey. If a site is unable to provide data via Dropbox, then an alternate method of data sharing maybe employed. Approved methods include mailing and faxing documents or through secure email.

All serious adverse events (SAE) (including death and hospitalization), premature withdrawal, and emergency treatment disclosures must be reported to the project program manager and [name] at the Lahey Hospital & Medical Center within one working day of site becoming aware of the event. Sites will notify [name] and the project program manager by emailing [[contact]](mailto:[contact]). Please include Site Name, Patient study ID, SAE event term, grade and pertinent de-identified source documents. Applicable SAE forms should be completed in the electronic data capture system (EDC) within one week of their occurrence and updated as new information becomes available.

A data monitoring committee comprised of [name] along with two Co-Investigators from Lahey Hospital will review all Adverse Events on a quarterly basis. All Serious Adverse Events will be reviewed as they occur in real time.

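### Section 12.4.3 removes pain-management admissions from the SAE definition with no exception for pain caused by protocol treatment, which contradicts 12.4.1

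*Combined protocol and SAP*

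**What the plan says.** Section 12.4.1 lists the criteria for a serious adverse event. One is an adverse event that "Requires in-subject hospitalization or prolongation of existing hospitalization". The same list removes events caused by disease progression, but only where progression is beyond doubt the cause. Section 12.4.3 opens with "The following types of hospitalizations do not constitute SAEs" and gives three items:

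- "Hospitalization or Emergency room visits secondary to expected cancer morbidity";
- "Admission for palliative care or pain management";
- planned surgical admissions.

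The first item is limited to morbidity from the cancer. The second has no limit of cause or relatedness.

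The SAE label triggers three things. Section 12.4.4, repeated in 18.2, requires a report to the sponsor within one working day. Section 12.4.2 sends events that are both serious and related to the IRB within 10 days or per institutional policy. Section 18.2 says "All Serious Adverse Events will be reviewed as they occur in real time", whereas adverse events in general are reviewed quarterly.

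Section 10.1 puts "Abdominal pain" first among four expected toxicities of TACE. Section 10.2 lists abdominal discomfort among the acute toxicities of SBRT.

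**The concern.** Pain that needs admission is a foreseeable serious consequence of the treatments under comparison, and the pain item takes it out of the SAE definition whatever its cause. A site that follows 12.4.1 and a site that follows 12.4.3 will classify the same readmission differently, in a non-blinded trial where toxicity is a secondary endpoint.

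The exclusion also acts before causality is judged. Section 12.4.1 asks investigators to assess the relatedness of SAEs. An admission already declared not to be an SAE never comes to the serious-and-related test in 12.4.2. At stake are the speed of the safety signal and the accuracy of any SAE tally reported by arm.

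**Working it through.** The plan states no figure that tests this point, so the main check sets the rules side by side for one case: a patient discharged after protocol treatment and newly admitted for treatment-related abdominal pain.

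1. **12.4.1, hospitalization criterion.** The adverse event required admission, so it is an SAE.
2. **12.4.1, progression exclusion.** Progression is not the cause, so this does not apply.
3. **12.4.3, first item.** The pain comes from treatment and not from the cancer, so on its face this does not apply.
4. **12.4.3, second item.** The admission is for pain management, so it is not an SAE. This contradicts step 1, and nothing in 12.4 says which rule prevails.
5. **Consequence if step 4 is followed.** There is no one-working-day report (12.4.4, 18.2), no IRB report as serious and related (12.4.2) and no real-time review (18.2).
6. **What still captures the event.** Section 12.3.1 collects all adverse events of grade 3 or higher, with attribution, and also abdominal pain, nausea, vomiting and fatigue of grade 2 or higher. Section 18.2 has these reviewed quarterly. The adverse-event paragraph of section 17 compares them by arm.

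The nearest safety figure in the plan is in 17.2.3: the chance of seeing at least one toxicity among 98 patients. It reproduces as 1 − 0.95^98 = 0.993 and 1 − 0.97^98 = 0.949, against the stated 99% and 95%. It concerns toxicities, which are still collected, so the exclusion does not undermine it.

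**Size, on assumed values only.** Let r be the rate of treatment-related admission, the same in both arms, and s the share of those admissions that are for pain management. With 98 patients per arm (17.2.3), expected SAEs counted = 98 × r × (1 − s).

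| r | True admissions per arm | s, TACE / SBRT | Counted, TACE | Counted, SBRT |
|---|---|---|---|---|
| 5% | 4.9 | 50% / 10% | 2.5 | 4.4 |
| 10% | 9.8 | 50% / 10% | 4.9 | 8.8 |
| 10% | 9.8 | 50% / 50% | 4.9 | 4.9 |
| 10% | 9.8 | 10% / 50% | 8.8 | 4.9 |
| 20% | 19.6 | 50% / 10% | 9.8 | 17.6 |

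For example, 98 × 0.10 × 0.5 = 4.9 and 98 × 0.10 × 0.9 = 8.8. With equal true rates, the direction of any distortion depends wholly on the pain shares, and the documents give neither rates nor shares.

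**The case against.** The strongest reply is that the planned toxicity comparison hardly depends on the SAE label. No SAE count is a named endpoint. Section 10.3 bases the toxicity analysis on grade 2 and higher, and abdominal pain of that grade is collected by name. Pain bad enough for admission would ordinarily be in that comparison. This stands, and it confines the point to seriousness, speed and the SAE tally.

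There are also other routes to attention. Section 12.4.4 leaves room for medical judgment on expedited reporting, the life-threatening and important-medical-event criteria remain in 12.4.1, and 18.2 asks for source documents within a week of each visit. Waiting a full quarter is thus a worst case for committee review. These routes rely on discretion or on central detection, however, and do not remove the contradiction.

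The exclusion is also narrow. Its wording covers admission and not prolongation, so a longer stay for pain after TACE, where 5.3 already keeps patients in hospital, arguably remains an SAE. Admissions for nausea, vomiting, fatigue, abscess or bleeding match no item in 12.4.3. A reader might infer that treatment-related hospitalizations in general escape SAE review; the text does not support that.

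A reader might also infer that liver decompensation after SBRT could be hidden under the first item. That item is limited to cancer morbidity, and section 10.3 points the other way for patients with Grade 4 enzyme elevation or early signs of liver injury: "If no tumor progression is documented in these subjects, liver injury will be presumed to be treatment related". Section 8.1 also calls for imaging to separate progression from toxicity when liver tests rise sharply. That inference rests on possible misclassification by a site, not on the rule as written.

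**Conclusion.** The point holds in a limited form. Sections 12.4.1 and 12.4.3 give opposite answers for a new admission for treatment-related pain, and the one-working-day rule in 12.4.4 does not resolve it. Followed as written, 12.4.3 costs the event its seriousness flag, its rapid reporting and its place in the SAE count. It does not cost the event its place in the adverse-event data.

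The size cannot be derived from the documents. If 5% to 20% of 98 patients in an arm had a related admission and half were for pain, between 2.5 and 9.8 SAEs would go unflagged in that arm; both inputs are assumptions.

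It is tempting to say that the under-count falls mainly on TACE. That is plausible: pain heads the TACE list, and the background says SBRT needs no hospitalization. It is not established, because SBRT lists abdominal discomfort and no admission rates by arm are given. The DEB-TACE results in section C do not fill the gap. "Post-embolization syndrome was observed in all subjects" says nothing about readmission. The 3.2% severe complication rate was one cholecystitis and one liver abscess among 62 subjects, and the 11.4% is an overall treatment-related complication rate.

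**What to change.** Reconcile 12.4.3 with 12.4.1 and 12.4.4 by adding one sentence to 12.4.3, for example: these exclusions apply only when the event is judged not related to protocol treatment; an admission for a treatment-related adverse event is reported as an SAE. Relatedness is then judged before an exclusion is applied, and the sentence gives the pain item a causal condition, as the progression exclusion already has. Carry the same sentence into the operations manual so that sites classify alike. A planned recovery stay after TACE is not itself an adverse event and would not be affected.

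The cost is a few more SAE forms and a slightly higher reported SAE rate. Treatment, visits, sample size and the primary analysis do not change.
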